10.1 Statistical and Analytical Plans

A statistical analysis plan will be prepared and finalized prior to database lock of the study. The statistical analysis plan will include full details of all planned statistical analyses and the dose selection strategy.

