10.6 Methods of Analysis

The safety and efficacy variables of each dose of NH002 will be presented using descriptive statistics. A series of selection rules based on efficacy and safety will be applied to determine the maximum tolerated dose. If no single NH002 dose shows a clear benefit in safety or efficacy, the lowest dose of NH002 will be selected.

Secondary endpoints will be summarized by descriptive statistics. Graphical presentations of the data will be provided, where appropriate.

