10.8 Determination of Sample Size

Each of the expected 36 completed subjects will receive 1 dose of NH002 (with 12 subjects per NH002 cohort). As this is a dose finding study, a formal sample size calculation was not required. The number of subjects dosed within each cohort is based on safety, with the objective of exposing the lowest possible number of subjects to the investigational agent, while still being able to assess safety.

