1.4. Objectives and Endpoints

Objectives	Endpoints
Primary	
To evaluate the safety and tolerability of 3 different ascending doses of NH002. 
Treatment Emergent Adverse event (TEAE) reporting and changes in physical examination findings, vital signs (VS), clinical laboratory evaluations, other laboratory evaluations, oxygen saturation, and electrocardiograms (ECGs).
Secondary	
To evaluate the preliminary diagnostic efficacy of NH002 as a contrast agent in echocardiography. 
The percentage of subjects with moderate or complete LVO, defined by an LVO grade of 2 (moderate) or 3 (complete), as assessed by the blinded central reader(s);The percentage of subjects with complete LVO, defined by an LVO grade of 3 (complete), as assessed by the blinded central reader(s);The change from baseline on the left ventricular endocardial border delineation (LVEBD) score, defined using a standard 12-segment model, as assessed by the blinded central reader(s). The LV endocardium of the 4- or 2-chamber apical views are divided into 6 segments, with 2 basal, mid- and apical segments in each view. For each segment, LVEBD is graded as follows: 0 = inadequate border (border not visible); 1 = sufficient (border barely visible); 2 = good (border clearly visible). A total delineation score (0-24) is obtained by adding the scores from the 6 individual segments in each of the 2 views;The changes from baseline on LVEBD score of subjects with suboptimal LVEBD at baseline, as defined by 2 or more contiguous segments of 6 segments that cannot be visualized reliably in either the apical 4- and/or the 2-chamber view, as assessed by the blinded central reader(s);

	
• The duration of clinically useful contrast calculated by measuring the time between the disappearance of shadowing effect (useful effect starts) and the time when moderate or full LV enhancement and contrast enhancement are no longer adequate (useful effect ends), as assessed by the blinded central reader(s).
--	--

2. Statistical Hypotheses

Not applicable.

3. Sample Size Determination

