5.4.1.2. Main analytical approach

- LVO Grade

A pair of apical 4-chamber and 2-chamber view images in each of the pre-injection and post-injection imaging sessions will be subjected to LVO grade assessment by central reading.

The highest LVO Grade among the pair of apical 4-chamber and 2-chamber view images of pre-injection and post-injection will be summarized and presented by each dose group and overall. When the LVO grades of both apical 4-chamber and 2-chamber view images are the same, the LVO grade of the apical 4-chamber view image will be used.

The following descriptive statistics will be summarized and presented:

- Number and percentage of subjects in each LVO Grade.
- Number and percentage of subjects with moderate or complete LVO.

In addition, the bar chart for Cumulative Percent of LVO Grade will be presented by pre-dose and post-dose groups in each cohort and overall.

Two LVO grades obtained for each session along with the corresponding times of images used will be listed.

- Table 12.1.1: Summary of LVO Grade, Full Analysis Set
- Figure 12.1.2: Cumulative Percent of LVO Grade, Full Analysis Set
- Table 12.2.1: Summary of LVO Grade, Per Protocol Set
- Figure 12.2.2: Cumulative Percent of LVO Grade, Per Protocol Set
- Listing 06.1: Image Evaluation - LVO Grade, Safety Set

- LVEBD Score

The descriptive statistics (n, mean, standard deviation, median, minimum, maximum, and 95% CI) of LVEBD score for pre-injection, post-injection and the change from baseline will be summarized and presented by each dose group and overall. LVEBD scores for subjects with suboptimal LVEBD at baseline (as defined by 2 or more contiguous segments of 6 segments that cannot be visualized reliably in either the apical 4- and/or the 2-chamber view) will also be summarized.

Moreover, the boxplots of the LVEBD score for pre-injection, post-injection and the change of LVEBD score will be presented by each cohort and overall.

Likewise, for subjects with suboptimal LVEBD at Baseline (as defined by 2 or more contiguous segments of 6 segments that cannot be visualized reliably in either the apical 4- and/or the 2-chamber view), the boxplots of the LVEBD Score for pre-injection, post-injection and the change of LVEBD score will be presented by each cohort and overall.

- Table 13.1.1.1: Summary of LVEBD Score, Full Analysis Set
- Figure 13.1.1.2: LVEBD Score, Full Analysis Set
- Figure 13.1.1.3: Change of LVEBD Score, Full Analysis Set

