- Table 13.1.2.1: Summary of LVEBD Score, Per Protocol Set
- Figure 13.1.2.2: LVEBD Score, Per Protocol Set
- Figure 13.1.2.3: Change of LVEBD Score, Per Protocol Set
- Table 13.2.1.1: Summary of LVEBD Score for Subjects with Suboptimal LVEBD at Baseline (as defined by 2 or more contiguous segments of 6 segments that cannot be visualized reliably in either the apical 4- and/or the 2-chamber view), Full Analysis Set
- Figure 13.2.1.2: LVEBD Score for Subjects with Suboptimal LVEBD at Baseline (as defined by 2 or more contiguous segments of 6 segments that cannot be visualized reliably in either the apical 4- and/or the 2-chamber view), Full Analysis Set
- Figure 13.2.1.3: LVEBD Score for Subjects with Suboptimal LVEBD at Baseline (as defined by 2 or more contiguous segments of 6 segments that cannot be visualized reliably in either the apical 4- and/or the 2-chamber view), Full Analysis Set
- Table 13.2.2.1: Summary of LVEBD Score for Subjects with Suboptimal LVEBD at Baseline (as defined by 2 or more contiguous segments of 6 segments that cannot be visualized reliably in either the apical 4- and/or the 2-chamber view), Per Protocol Set
- Figure 13.2.2.2: LVEBD Score for Subjects with Suboptimal LVEBD at Baseline (as defined by 2 or more contiguous segments of 6 segments that cannot be visualized reliably in either the apical 4- and/or the 2-chamber view), Per Protocol Set
- Figure 13.2.2.3: LVEBD Score for Subjects with Suboptimal LVEBD at Baseline (as defined by 2 or more contiguous segments of 6 segments that cannot be visualized reliably in either the apical 4- and/or the 2-chamber view), Per Protocol Set
- Listing 06.2: Image Evaluation - LVEBD Score, Safety Set
- Duration of Clinically Useful Contrast Enhancement

The duration of clinically useful contrast enhancement is the number of minutes between start time point and end time point of useful contrast imaging, rounded to one decimal place.

The formula for duration calculation is as below.

Duration (Minutes)=(End Time (hh:mm:ss) of Useful Contrast Imaging - Start Time (hh:mm:ss) of Useful Contrast Imaging)/60, rounded to one decimal place.

The descriptive statistics (n, mean, standard deviation, median, minimum, maximum, and 95% CI) of the duration of clinically useful contrast enhancement will be presented by each dose group and overall. The unit of duration is minute.

Furthermore, the boxplots of duration of clinically useful contrast enhancement will be presented by each cohort and overall.

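### The dose-selection rule compares doses on efficacy, but the SAP contains neither the promised selection strategy nor any between-dose estimate

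*SAP*

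**What the plan says.** Protocol 10.6 (Methods of Analysis) contains the selection rule. It states that "A series of selection rules based on efficacy and safety will be applied to determine the maximum tolerated dose", and then: "If no single NH002 dose shows a clear benefit in safety or efficacy, the lowest dose of NH002 will be selected". It lists no selection rules and does not define a clear benefit. Protocol 10.1 says where the detail belongs: "The statistical analysis plan will include full details of all planned statistical analyses and the dose selection strategy".

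The SAP has no dose-selection section. Section 2 gives "Not applicable" for statistical hypotheses. Section 5.1 provides descriptive statistics by dose group and overall, with a 95% CI for continuous efficacy variables and counts and percentages for categorical ones. Section 5.4.1.2 applies this as follows:

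- **Duration of useful contrast:** descriptive statistics with a 95% CI "of the duration of clinically useful contrast enhancement will be presented by each dose group and overall", plus boxplots by cohort.
- **LVEBD score and its change:** the same set of statistics and plots.
- **LVO:** "Number and percentage of subjects with moderate or complete LVO", the distribution over grades, and a cumulative bar chart. No interval is planned.

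No output estimates a difference between doses. SAP 5.6 adds that the tables for the Dose Escalation Committee show only the dose of the cohort concerned, and leaves the committee's timelines and responsibilities to a separate Charter.

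Protocol 10.8 plans 36 subjects, "with 12 subjects per NH002 cohort", and explains: "As this is a dose finding study, a formal sample size calculation was not required".

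**The concern.** Whether one dose shows a clear benefit can be judged only by setting the doses against each other. The quantity that matters is a difference between doses and its uncertainty. The SAP quantifies uncertainty within each dose for duration and LVEBD, gives none for LVO, and gives none between doses for anything. The pooled overall column does not help, because it averages over the doses being compared.

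The document that was to state the strategy does not state it, so whoever applies 10.6 must decide after seeing the data what counts as clear. Two careful readers of the same tables could disagree. One common informal reading, checking whether separate intervals overlap, is much stricter than it looks. Because 10.6 has a default, an unclear comparison has a consequence: the lowest dose is taken unless safety or efficacy separates the doses.

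**Working it through.** **Inputs from the documents.** 3 cohorts x 12 = 36 subjects (Protocol 10.8), at 2.5, 5.0 and 10.0 μl/kg. No alpha, power, SD or effect size is stated, so there is no sample-size figure to reproduce.

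**Assumptions.** Normal data, a common SD (s), t-based two-sided 95% intervals, all 12 subjects per dose evaluable, and a true highest-minus-lowest difference between 0.5s and 1.5s.

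**Step 1: half-width of each planned interval.** t(0.975, 11)/√12 x s = 2.201/3.464 x s = 0.635s.

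**Step 2: difference at which two such intervals just separate.** With equal sample SDs, 2 x 0.635s = 1.27s.

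**Step 3: difference at which a 95% CI for the difference excludes zero.** t(0.975, 22) x √(2/12) x s = 2.074 x 0.408s = 0.85s. Intervals that just touch correspond to t = 1.271/0.408 = 3.11 on 22 df, p = 0.005. In simulation with no true difference, the intervals fail to overlap in 0.56% of trials, against a nominal 5%.

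**Step 4: chance of separating the highest and lowest doses** (200,000 simulated trials; the difference-CI column agrees with the exact noncentral t).

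| True difference | Separate CIs do not overlap | Difference CI excludes 0 |
|---|---|---|
| 0.5s | 5% | 22% |
| 0.8s | 16% | 47% |
| 1.0s | 30% | 65% |
| 1.2s | 46% | 80% |
| 1.5s | 72% | 94% |

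For 80% detection, the true difference must be about 1.62s by non-overlap and 1.20s by the difference CI.

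**Step 5: what this could do to the default.** Suppose efficacy alone decided, the middle dose lay halfway between the others, and a higher dose counted as clearly better only if its interval lay wholly above that of the lowest dose. At a highest-minus-lowest difference of 1.0s the default would then apply in 69% of trials, against 33% using pairwise difference CIs. At 1.5s the figures are 27% and 6%.

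**Step 6: does a dose trend add much?** The slope per doubling over 36 subjects has SE s/√24 = 0.204s and half-width t(0.975, 33) x 0.204s = 0.415s. Over the full range of two doublings this is 0.83s, against 0.85s for the simple difference. The chance of excluding zero at 1.0s is 66% against 65%, so the trend adds very little.

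**Step 7: LVO.** For illustrative counts of 6/12 and 12/12, the difference is 50 points with a Newcombe 95% CI of 15 to 75. With true rates of 50% and 90%, that interval excludes zero in 60% of trials. At the 87% and 91% that Protocol 5.3 cites for another perflutren agent (not planning values for NH002), it does so in about 2%. On a normal approximation, 80% power would need about 960 per arm.

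**The case against.** A reader might infer that the planned tables make dose selection rest on interval overlap, hide a dose effect and so push the choice to the lowest dose. The documents do not support that.

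- No section says that a clear benefit is judged by overlap. Steps 2 to 5 measure one possible reading.
- LVO has no planned intervals to overlap. A table showing, say, 50%, 75% and 100% would display a gradient.
- For duration, the means, SDs and boxplots by dose also show a gradient, and a reader could compute a difference CI from them.
- The rule in 10.6 covers safety as well as efficacy, so efficacy results alone do not force the default.
- Protocol 10.6 is not the only place where efficacy enters a dose decision. Sections 7.1 and 7.5.1.2 allow early escalation when 4 subjects show no visible contrast effect and no safety concern, and 7.3.1 refers to a utility function based on LVO.

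There is also a fair general defence. Efficacy is secondary and preliminary, the study is phase 1, descriptive analysis is a declared choice, and the cohorts are sequential without randomisation. An interval for a between-dose difference could therefore lend false precision to a contrast that mixes dose with period or case mix. The Charter, which is not available here, may say more about the committee's role.

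These points limit the size of the problem but do not remove it. A difference with a CI is estimation, so it leaves SAP Section 2 intact. The SAP already reports CIs for continuous efficacy variables, just not for the quantity that 10.6 uses. Protocol 10.1 assigns the strategy to the SAP, not to the Charter.

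**Conclusion.** The point holds as a modest gap that is cheap to close. Two facts are documented: the SAP lacks the dose selection strategy that Protocol 10.1 promises, and it plans no between-dose estimate for any efficacy endpoint although 10.6 turns on a comparison of doses.

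The numerical loss is conditional. Only if the doses were compared by CI overlap would the threshold be about 1.27 SD instead of 0.85 SD, with 30% instead of 65% of trials separating two doses at a true difference of 1.0 SD. These figures rest on assumed normality, a common SD, assumed effect sizes and 12 evaluable subjects per dose.

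Part of the difficulty is the sample size itself. Even with difference CIs, true differences below about 1.2 SD are detected with less than 80% probability, and near-ceiling LVO rates stay unresolved. No view is taken on which dose is right.

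**What to change.** Before database lock:

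1. **Add to SAP 5.4.1.2, labelled exploratory:** pairwise between-dose differences with 95% CIs for duration and for LVEBD change, and differences in the two LVO responder percentages (moderate or complete; complete) with Newcombe 95% CIs. State that the intervals are not adjusted for multiple contrasts. A slope per doubling of dose is optional, since it adds little precision.
2. **For duration, also report by dose how many subjects still had useful contrast when imaging ended.** Protocol 7.1.1 ends post-injection imaging at 10 minutes, so longer durations may be cut off there and differences in means would then be distorted.
3. **Write the dose selection strategy promised in Protocol 10.1.** It should say that the efficacy part of a clear benefit is read from these difference estimates, together with the safety results, and it should be reconciled with the wording of Protocol 10.6. The content of any clinical threshold is for the sponsor and is not proposed here.

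The cost is a short addition to the SAP text and a few tables, with no new data and no formal hypothesis. The downside is that the contrasts may reflect period or case mix as well as dose, and the text must say so beside each table.

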5.5. Analysis of Other Variables

5.5.1. Telephone Call

Telephone Call will be listed by subject identity, visit, day, date of contact, successfully reaching the subject, any new or changed symptoms experienced since last visit, and any new or changed medications used since last visit.

- Listing 09: Telephone Call, Safety Set

5.6. Dose Escalation Committee (DEC)

To enhance the safety and integrity of the study data, a DEC will evaluate clinical, laboratory, and electrocardiographic safety before advancing to the next dose level. It will consist of sponsor personnel, the independent medical monitor, and the investigator(s) at the study site.

A sentinel review approach will be followed whereby the first review will be conducted at the end of the safety follow-up observation period for the first subject treated in Cohort 1 to determine if subsequent subjects may be dosed in the cohort. In order to review all cumulative safety data for Cohort 1, the next review will be conducted at the end of the safety follow-up observation period for the last subject treated in Cohort 1. This sentinel review approach will continue to be followed for all successive cohorts (i.e., Cohort 2 and Cohort 3), in order to review safety data and to provide a recommendation on study continuation, recommended dose, or early termination in case there is a concern regarding safety. This will be repeated until the highest dose level has been evaluated.

The tables and listings for DEC will follow the shells that only present the data of the dose in each cohort.

Further details regarding timelines and specific responsibilities of the DEC will be provided in a separate Charter².

5.7. Handling of Missing Data

As all treatments are scheduled in a single study visit, the level of missing data for the primary endpoint is anticipated to be small. Every attempt will be made to avoid missing data. All subjects will be used in the safety analysis, using non-missing data available. No imputation process will be used to estimate/substitute missing data.

6. References

1. Protocol Deviation Handling Plan (PDHP) Version 1.0.
2. The Dose Escalation Committee Charter Version 1.0.
3. NH002-LV_Protocol_v1.0.
4. Data Transfer Specification TRUS-10006193, ECHO Final 3.0, 16 Sep 2020.
5. Specification of Suboptimal Echocardiogram Data Transfer_20201116_TRUST.

7. Appendices

7.1. Appendix 1: List of Abbreviations

- **List of Abbreviations**

Abbreviations	Description of abbreviations
AE	Adverse Event
ALP	Alkaline Phosphatase
ALT	Alanine Aminotransferase
ANC	Absolute Neutrophil Count
aPTT	Activated Partial Thromboplastin Time
AST	Aspartate Aminotransferase
BMI	Body Mass Index
β-HCG	Beta-Human Chorionic Gonadotropin
CBC	Complete Blood Count
CI	Confidence Interval
CS	Clinically Significant
DBP	Diastolic Blood Pressure
DEC	Dose Escalation Committee
EBD	Endocardial Border Delineation
ECG	Electrocardiogram
EOT	End of Treatment
FAS	Full Analysis Set
HCT	Hematocrit
HR	Heart Rate
ICF	Informed Consent Form
ICH	International Council for Harmonisation
IV	Intravenous
LV	Left Ventricle [Ventricular]
LVEBD	Left Ventricular Endocardial Border Delineation
LVO	Left Ventricular Opacification
MCH	Mean Cell Hemoglobin
MedDRA	Medical Dictionary for Regulatory Activities
NCS	Not Clinically Significant
PD	Protocol Deviation
PDHP	Protocol Deviation Handling Plan
PE	Physical Examination
PLT	Platelet Count
PP	Per Protocol
RR	Respiratory Rate
SAE	Serious Adverse Event

Abbreviations	Description of abbreviations
SBP	Systolic Blood Pressure
SpO ₂	Peripheral Oxygen Saturation
SS	Safety Set
TEAE	Treatment-Emergent Adverse Events
TT	Thrombin Time
VS	vital signs
WBC	white blood cell

7.2. Appendix 2: Adds to Protocol-Planned Analyses

7.2.1. Re-screened Subjects

For re-screened subjects, information is taken from the last re-screening visit instead of the screening visit.

The number of subjects re-screened are summarized in Table 01.1: Summary of Subject's Disposition.

7.2.2. External Data Transfer

The external data transfer process not described in the study protocol³ is illustrated as below.

The efficacy data including LVO grade, LVEBD score, and the useful contrast imaging start time/ end time assessed by the blinded central readers (assigned by [REDACTED] Inc.) are not from the record on CRF but be transferred by [REDACTED] Inc. Further details are provided in the Data Transfer Specification⁴.

For those subjects are suboptimal LVEBD at baseline, as defined by 2 or more contiguous segments of 6 segments that cannot be visualized reliably in either the apical 4- and/or the 2-chamber view, Trust Bio-Sonics, Inc. transfers the Suboptimal Echo Classification Data according to the Specification of Suboptimal Echocardiogram Data Transfer⁵.

All external data is cleaned and reconciled to ensure the data correctness.

